6.3.3 Safety Analysis

All subjects entered into the study at Visit 1 will be included in the safety analysis. The frequencies of AEs by type, body system, severity and relationship to study intervention type will be summarized. SAEs (if any) will be described in detail.

AE incidence will be summarized along with the corresponding exact binomial 95% two-sided confidence intervals.

6.4 Sample Size and Power

This study will compare the PSM VR intervention to treatment-as-usual (TAU) in a total of 96 adolescents and adults with ASD, in two separate studies (i.e., n=48 per study). The most relevant study to date (Didehbani, Allen, Kandalaft, Krawczyk, & Chapman, 2016) included 30 7-16 year-olds with ASD in a pre/post virtual reality intervention to improve social cognitive skills. This study suggested a medium-to-large within-group effect of VR intervention on emotion recognition (Cohen's d = .63), but did not compare two interventions. Sensitivity analysis using G*Power indicated that intervention differences using our proposed sample size (N=48 per group) will be detected with a critical t of 1.99, and that we will be able to detect differences with effect sizes of Cohen's d = .74 or larger. Data will be behaviorally coded from video interactions and correct answers marked on knowledge tests. Scores will be summed, averaged, and examined for normality at the group level. Normally distributed data will be analyzed using parametric statistics (e.g., ANOVA, regression, Pearson correlation), and data that do not meet normality assumptions will either be transformed or will be analyzed using nonparametric statistical tests (e.g., Chi-square, Spearman correlation). Analyses will be corrected for comparisons. To compare PSM to BE SAFE, an Analysis of Variance (ANOVA) with Group (PSM VR Intervention, BE SAFE The Movie Video Modeling Intervention) as a Between-Subjects factor will be conducted for Live Interaction data. A separate ANOVA (or comparable statistical test) will be conducted for Questionnaire data. Relevant potential covariates include knowledge of police interactions at intake, sensory sensitivity scores, verbal abilities, and chronological age.

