Individuals with social communication disabilities like ASD may be particularly susceptible to poor police interaction outcomes due to difficulty reading social cues (American Psychiatric Association, 2013), variable verbal ability (Tager-Flusberg & Kasari, 2013), heightened anxiety (Sukhodolsky et al., 2008), and reduced executive control (Blijd-Hoogewys et al., 2014). The presence of intellectual disability (ID) is associated with greater risk of injury during police interactions (Perry & Carter-Long, 2016), and approximately 30% of individuals with ASD also have ID (CDC, 2012). Rava et al. (2017) reported that elevated externalizing behaviors in U.S. teens with ASD are associated with police contact. Similarly, Tint et al. (2017) reported that instances of aggressive behavior are the most common cause of contact between police and Canadian adults with ASD.

Existing intervention approaches relevant to interactions with law enforcement for individuals with ASD have not been shown to be effective. The effort to promote optimal social and community living skills in young adults with ASD has led researchers to investigate strategies such as story-based interventions and video modeling. Social StoriesTM is the most well-known story-based intervention. While a systematic review of Social StoriesTM found positive benefits for various social outcomes (Karkhaneh et al., 2010), a meta-analysis found Social StoriesTM to be of limited effectiveness in addressing social difficulties (Kokina and Kern, 2010).

Video modeling intervention was found to be moderately effective (Hong et al., 2016) and described as an evidence-based practice for daily living skills (Hong et al., 2015) for individuals with ASD. BE SAFE The Movie uses a video modeling approach to support more effective interactions between individuals with ASD and law enforcement officers. This program has been used in communities across the country and is featured as a safety resource by Autism Speaks. However, the efficacy and effectiveness of the BE SAFE intervention have not yet been experimentally examined and there are currently no evidence-based programs specifically designed to train police safety skills in individuals with ASD.

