3.1.2 Cycle A – Laboratory-Based Efficacy Study

In the first year of the study, an efficacy study will be conducted at the Center for Autism Research. Subjects will be randomized to the VR intervention or to the video modeling control condition (with stratification, see *Study Procedure*). Subjects in each condition will undergo a baseline assessment of police interaction skills via a live role play with a study staff member and three sessions of their assigned intervention within an approximately six-week period. At the end of Visit 3, subjects' police interaction skills will be assessed via a live interaction with a police officer.

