3.1.3 Cycle B – Virtually-Based Efficacy Study

In the second year (after the completion of Cycle A), a virtually-based efficacy trial will be conducted by CHOP staff via videoconference. Subjects will be randomized to the VR intervention or to the treatment-as-usual condition (with stratification, see *Study Procedure*). Subjects in each condition will undergo a baseline assessment of police interaction skills via a novel pre-/post-intervention assessment and three sessions within an approximately six-week period. At the end of Visit 3, subjects' police interaction skills will be assessed. There will be an additional follow-up visit approximately 4 weeks post-training, for all participants, to readminister outcome measures, as an assessment of maintenance of learning.

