3.2.2 Total Number of Study Sites/Total Number of Subjects Projected

The study will be conducted at approximately two investigative sites in the United States. Cycle A of the study will be conducted at the Center for Autism Research at CHOP, while Cycle B will be conducted virtually using CHOP approved, HIPPA compliant video conferencing software.

Recruitment will stop when approximately 48 evaluable subjects complete each phase of the study. It is expected that approximately 400 subjects will be enrolled to produce 96 evaluable subjects.

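### Section 6.4 sizes one 96-subject VR versus TAU comparison; the design is two 48-subject studies with different controls, so d = .74 fits neither cycle

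*Combined protocol and SAP*

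**What the plan says.** The opening of section 6.4 describes a single comparator for the whole trial: "This study will compare the PSM VR intervention to treatment-as-usual (TAU) in a total of 96 adolescents and adults with ASD". The same sentence then divides the total "in two separate studies (i.e., n=48 per study"). Two sentences later the G*Power sensitivity analysis is described as "using our proposed sample size (N=48 per group"), with a critical t of 1.99 and a detectable Cohen's d of .74 or larger. Alpha, sidedness, power and allocation ratio are not given.

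The design sections describe something else. For Cycle A, section 3.1.2 says "Subjects will be randomized to the VR intervention or to the video modeling control condition". For Cycle B, section 3.1.3 says "Subjects will be randomized to the VR intervention or to the treatment-as-usual condition". Section 3.2.2 confirms the size: "Recruitment will stop when approximately 48 evaluable subjects complete each phase of the study". Section 6.3.2 makes VR versus BE SAFE the Cycle A comparison, and section 6.4 itself later specifies an ANOVA of PSM against BE SAFE. Section 9.6 states that the two cycles are distinct populations.

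The only effect size cited is from an earlier VR study, described as a "medium-to-large within-group effect of VR intervention on emotion recognition (Cohen's d = .63), but did not compare two interventions".

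**The concern.** Two statements in section 6.4 do not match the design. The first is the comparator: about 48 subjects, not 96, enter a comparison with TAU, and the Cycle A comparison with video modeling, which the abstract names as the primary objective, is missing from the opening description. The second is the sample size behind the detectable effect. The section gives 48 both as the number per study and as the number per group. If 48 is the study total, no comparison has 48 in each arm.

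At stake is the one figure that tells a reader what each study can show. If d = .74 was worked out for twice the subjects that either cycle has, both cycles are less sensitive than the plan states, and a null result in either would be given more weight than it can bear.

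**Working it through.** **Inputs.** 48 subjects per study and, in conflict, 48 per group (6.4); about 48 evaluable per cycle (3.2.2); critical t 1.99 and d = .74 (6.4). Assumed because not stated: 1:1 allocation, two-sided 5%, unadjusted two-sample t test (equivalent to the planned two-group ANOVA), and 48 analysed per cycle.

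**Method.** With n per arm, df = 2n − 2 and noncentrality = d × √(n/2). Power is the probability that a noncentral t with these parameters exceeds the two-sided critical value in either direction. The detectable d is found by solving for the required power. A hand approximation is d ≈ (t₀.₉₇₅ + t_power) × √(2/n).

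**Step 1: reproduce the plan's figure.** Take n = 48 per arm, df = 94.
- Critical t = 1.9855, which rounds to 1.99.
- Detectable d at 95% power = 0.7435, which rounds to .74. By hand: (1.9855 + 1.6612) × √(2/48) = 3.6467 × 0.2041 = 0.744.
- At 80% or 90% power the same n gives 0.578 or 0.669, so 95% is the power level that fits.

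**Step 2: can a 48-subject study give the same figures?** No. A two-sided 5% critical t rounds to 1.99 only for df from 69 to 95, and 48 subjects in two arms give df = 46. A one-sided test at 24 per arm and 80% power gives d = 0.729, near .74, but its critical t is 1.68.

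**Step 3: recompute at each cycle's own size.** Take n = 24 per arm, df = 46.
- Critical t = 2.0129.
- Detectable d at 95% power, by hand: (2.0129 + 1.6787) × √(2/24) = 3.6916 × 0.2887 = 1.066; exact, 1.063.
- Noncentrality at d = .74: 0.74 × √12 = 2.563, against 0.74 × √24 = 3.625 at 48 per arm.

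| Quantity (two-sided 5%) | 48 per arm | 24 per arm |
|---|---|---|
| Critical t | 1.99 | 2.01 |
| Detectable d, 80% power | 0.58 | 0.83 |
| Detectable d, 90% power | 0.67 | 0.96 |
| Detectable d, 95% power | 0.74 | 1.06 |
| Power at d = .74 | 95% | 71% |

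**Step 4: how far the assumptions move this.** Adjusting for a baseline score with an assumed correlation of .3, .5 or .7 multiplies the detectable d by √(1 − r²). At 24 per arm this gives 0.79, 0.72 or 0.59 at 80% power, and 1.01, 0.92 or 0.76 at 95%. Section 6.4 promises a correction for multiple comparisons without specifying it; an illustrative alpha of 0.025 raises the 80% value from 0.83 to 0.92.

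**Step 5: does the type of control enter?** No. The formula contains n, alpha and power only. Keeping 48 per arm and changing the comparator from TAU to BE SAFE leaves the detectable d at .74.

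**The case against.** The best defence is that the opening is a drafting slip. Section 6.4 goes on to specify the PSM versus BE SAFE ANOVA, and sections 3.1.2 and 6.3.2 are clear, so the Cycle A analysis is not in doubt. That stands for the comparator label. It does not explain the per-group count of 48, which is built into the reported t and d. Pooling the cycles would give 48 VR and 48 control subjects, but no pooled analysis is specified: section 6.4 calls them separate studies, and they differ in control and in outcome (live officer or avatar).

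It can also be said that baseline adjustment could bring the detectable d back to .74 or lower at 80% power. That is possible, but the ANOVA as written has group as its only factor, covariates are listed as potential, and no correlation is given. At the 95% power implied by the plan's own figure, even r = .7 gives 0.76.

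Three stronger readings are tempting, and the documents do not support them.
- A reader might infer that the active control itself makes .74 too optimistic for Cycle A. It does not. An active control bears on which true difference is plausible, not on which difference is detectable. Section 1.3 does say that "Video modeling intervention was found to be moderately effective", but adds that BE SAFE itself has not been tested experimentally. Any power figure that subtracts a BE SAFE gain therefore rests on an assumed gain.
- A reader might infer that the cited .63 inflated the sizing. A sensitivity analysis takes no expected effect as input, .63 lies below .74, and the plan already says that it is within-group and that the source did not compare two interventions.
- A reader might infer that the plan would treat a non-significant Cycle A result as equivalence. No section says so; the stated hypothesis in 6.3.2 is superiority.

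**Conclusion.** The point holds as an error in the sizing statement that affects both cycles alike. The TAU label is wrong for about half the 96 subjects. The stated critical t and d belong to a comparison of 48 per arm that the design does not contain. At about 24 per arm the detectable d at the plan's implied 95% power is 1.06, not .74; at 80% power it is 0.83; and power at d = .74 is about 71% rather than 95%.

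This rests on 1:1 allocation, two-sided 5%, 48 analysed subjects per cycle and no covariate adjustment. The 5% two-sided level and 95% power are inferred, being the combination that returns both stated figures at 48 per group. Unequal allocation would lower sensitivity further; a strongly correlated baseline covariate would raise it. The .63 may stay as context, but should not be taken as an expected difference between VR and BE SAFE.

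**What to change.** Replace the first sentence of section 6.4 with: *Cycle A compares PSM VR with BE SAFE video modeling (n=48 total); Cycle B compares PSM VR with treatment-as-usual (n=48 total).*

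Replace the per-group count of 48, the critical t of 1.99 and d = .74 with values for each cycle at its actual per-arm n, stating alpha, sidedness, power and allocation. With 24 per arm and two-sided 5% these are t = 2.01 and d = 0.83 at 80% power, or 1.06 at 95%. If the sponsor relies on baseline adjustment or a multiplicity correction, the assumed correlation or adjusted alpha should be stated with the figure.

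Commit to reporting each cycle's arm difference with its 95% CI. Check section 6.1 at the same time: it also attaches TAU to the live assessment, which belongs to Cycle A.

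The cost is wording and a less favourable stated sensitivity. No extra subjects are needed.

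### The stated detectable effect (d = .74, critical t 1.99) assumes 48 per arm, but each two-arm study has about 48 in total, so that sensitivity is not delivered

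*Combined protocol and SAP*

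**What the plan says.** Section 6.4 (Sample Size and Power) sets the size of the programme as "in a total of 96 adolescents and adults with ASD, in two separate studies (i.e., n=48 per study". Section 3.2.2 agrees: "Recruitment will stop when approximately 48 evaluable subjects complete each phase of the study", which makes 96 over the two cycles.

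Each cycle has two arms. Section 3.1.2 says of Cycle A: "Subjects will be randomized to the VR intervention or to the video modeling control condition". Section 3.1.3 says of Cycle B: "Subjects will be randomized to the VR intervention or to the treatment-as-usual condition". For Cycle A, Section 6.4 plans "an Analysis of Variance (ANOVA) with Group (PSM VR Intervention, BE SAFE The Movie Video Modeling Intervention) as a Between-Subjects factor", which with two groups is equivalent to an independent two-sample t test.

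The same paragraph of Section 6.4 bases its sensitivity analysis on 48 participants in each group: "using our proposed sample size (N=48 per group) will be detected with a critical t of 1.99". From this the plan draws its claim about the smallest detectable effect: "we will be able to detect differences with effect sizes of Cohen's d = .74 or larger". It gives no alpha, sidedness or power. Later the paragraph says that analyses will be corrected for multiple comparisons, without naming the method or the comparisons covered.

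**The concern.** The paragraph uses 48 in two incompatible ways: first as the total for a study, then as the size of one arm. The recruitment rule in Section 3.2.2 shows that the total is what will be delivered, so the sensitivity analysis appears to have been run on twice the sample available for each comparison.

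This is the only quantitative justification of the sample size in the document. A reader would take it that each cycle has a high chance of detecting a difference of d = .74. If that is untrue, a null result in either cycle could be over-read as evidence against effects of that size.

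**Working it through.** **Inputs from the document**
- 48 participants per study, 96 overall (Sections 6.4 and 3.2.2).
- Two arms per cycle (Sections 3.1.2 and 3.1.3).
- Two-group between-subjects comparison (Section 6.4).
- Stated results: critical t 1.99 and detectable d = .74, at 48 per group (Section 6.4).

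**Inferred or assumed**
- Two-sided alpha of 0.05, inferred because it gives the stated critical t at 48 per arm.
- 95% power, inferred because of the levels tried (80, 85, 90 and 95%) it is the one that gives d = .74 at 48 per arm.
- 1:1 allocation, assumed. Section 9.1.1 gives no ratio.

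**Method.** Noncentral t for two independent groups, with df = n1 + n2 − 2 and noncentrality = d / √(1/n1 + 1/n2). For equal arms the noncentrality is d·√(n/2).

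**Step 1: reproduce the plan's figures at 48 per arm**
- df = 48 + 48 − 2 = 94; critical t = 1.986, which rounds to 1.99.
- Noncentrality at d = .74 is 0.74 × √24 = 3.63; power = 94.8%.
- Detectable d at 95% power = 0.743. At 80% power it would be 0.578, so the plan's .74 is not an 80%-power figure at this size.

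Both stated figures reproduce.

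**Step 2: repeat with 48 in total, 24 per arm**
- df = 24 + 24 − 2 = 46; critical t = 2.013.
- Noncentrality at d = .74 is 0.74 × √12 = 2.56; power = 70.9%.

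| | 48 per arm | 24 per arm |
|---|---|---|
| Critical t | 1.986 | 2.013 |
| Power at d = .74 | 94.8% | 70.9% |
| Detectable d, 80% power | 0.578 | 0.826 |
| Detectable d, 90% power | 0.669 | 0.956 |
| Detectable d, 95% power | 0.743 | 1.063 |

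**Step 3: can another reading of 48 give the stated pair?**
- A two-sided critical t that rounds to 1.99 needs df between 69 and 95. Any split of 48 between two arms has df 46, so this does not depend on 1:1 allocation.
- A paired or one-sample test on 48 has df 47 and critical t 2.012.
- A one-sided 0.05 test at 24 per arm gives d = 0.729 at 80% power, but its critical t is 1.68.
- Unequal splits lower the power at d = .74 further: 69.7% at 20:28 and 65.8% at 16:32.

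**Step 4: effect of a multiplicity correction (assumption).** If the planned correction were Bonferroni for two tests, alpha would be 0.025. At 24 per arm the critical t is then 2.317, power at d = .74 is 59.9%, and the detectable d at 80% power is 0.915.

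**The case against.** **The benchmark is inferred.** Section 6.4 states no power, so the contrast of 71% with 95% sets a computed figure against one the plan never gives. This stands as a caveat. Against a conventional 80%, the gap is 0.83 versus 0.74, smaller than 1.06 versus 0.74. At each of these power levels the detectable effect still exceeds the stated one.

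**Covariate adjustment could recover sensitivity.** Section 6.4 lists possible covariates, and Sections 6.3.1 and 9.1.1 plan adjustment for variables that differ between groups. Using the factor √(1 − r²) and ignoring the small loss of df, 24 per arm reaches d = .74 at 80% power if r = √(1 − (0.74/0.826)²) ≈ 0.44, and at 95% power if r = √(1 − (0.74/1.063)²) ≈ 0.72. This is possible, but the document gives no correlation and the stated critical t does not reflect such an analysis.

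**The analysed set could exceed 48.** Section 3.2.2 counts evaluable completers, while Section 6.3.2 analyses everyone randomized at Visit 1. About 30 per arm would give 80% power at d = .74. However, no number randomized per cycle is stated, and a critical t of 1.99 would need at least 69 + 2 = 71 analysed in a cycle.

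**Pooling the cycles would give 48 against 48.** Some wording blurs the cycles: Section 2.1 names both comparators in one objective, and Section 6.1 names the Live and Virtual scores together. But no pooled analysis is described. Section 6.4 calls the studies separate and specifies a stand-alone comparison with BE SAFE, and Section 9.6 treats the cycles as distinct populations. They also differ in control (Section 5.3), outcome assessment (Section 5.4.2) and IQ floor (Section 3.3.1).

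**The calculation is right for its input.** That is fair: the fault is the number entered, not the computation. The resulting claim is still wrong for the trial as planned.

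The d = .63 cited in Section 6.4 is not used as a benchmark here, because the plan describes it as a within-group effect.

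**Conclusion.** The concern holds. The stated sensitivity belongs to a comparison of 48 with 48, which the plan does not describe; each planned comparison has about 48 participants in all. The conflict between the two uses of 48, and the mismatch in critical t (2.01 rather than 1.99 on a two-sided 0.05 test), do not depend on the allocation ratio or the power level.

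The size of the shortfall rests on two-sided alpha 0.05, 1:1 allocation, an unadjusted comparison and 48 analysed per cycle. Under those assumptions the detectable effect is understated by 0.83 − 0.74 = 0.09 if 80% power was meant, and by 1.06 − 0.74 = 0.32 at the implied 95%. A multiplicity correction would widen the gap; a strong baseline covariate or a larger randomized set would narrow it. The document quantifies none of these. The statement must be corrected, because it is the only justification given for the sample size.

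**What to change.** Rewrite the sensitivity statement in Section 6.4 separately for each cycle:

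- Replace the 48-per-group figure with about 24 per arm (48 per cycle), and state the allocation ratio.
- State alpha, sidedness and power. On a two-sided 0.05 test the critical t is 2.01, and the detectable d is 0.83 at 80% power or 1.06 at 95%.
- If a baseline-adjusted analysis is adopted, also give the adjusted figure, 0.83 × √(1 − r²), with r labelled as an assumption. At r = 0.5 this is 0.83 × 0.866 = 0.72.
- If a multiplicity correction applies to the primary comparison, name it and give the detectable effect at the corrected alpha.
- State the expected number randomized per cycle, so that the calculation matches the intention-to-treat set.

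The cost is a change of protocol wording and a less favourable stated sensitivity. The correction itself requires no extra enrolment. Whether the corrected detectable effect is acceptable, or whether the sample should be reconsidered, is for the sponsor to decide.

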6 STATISTICAL CONSIDERATIONS

6.1 Primary Endpoints

The primary efficacy endpoints will be the change in post-treatment Live and Virtual Police Interaction Assessment Scores between the Virtual Reality Intervention and treatment-as-usual groups, and the change in scores between the Baseline Assessment and Virtual Police Interaction Assessment.

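### Section 6.4 promises a correction for multiple comparisons that it never defines, and its critical t (1.99) and detectable d (0.74) are those of one uncorrected test with 48 per group, not of the 48 per study planned

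*Combined protocol and SAP*

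**What the plan says.** **Multiplicity.** Section 6.4 says "Analyses will be corrected for comparisons". It does not say which analyses form the family, how many there are, what method applies, or whether the primary comparison is included. No other section fills this in.

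**Primary quantities.** Section 6.1 speaks of endpoints in the plural. It names the post-treatment interaction score compared between groups "and the change in scores between the Baseline Assessment and Virtual Police Interaction Assessment". Section 6.3.2 repeats the same pair for Cycle A with the Live assessment. Sections 6.2 and 6.3.2 add the knowledge questionnaire and, in Cycle B, the 4-week assessment, each with its own hypothesis of superiority.

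**Sensitivity analysis.** Section 6.4 bases it on "our proposed sample size (N=48 per group", says that differences "will be detected with a critical t of 1.99", and concludes that "we will be able to detect differences with effect sizes of Cohen's d = .74 or larger". Alpha, sidedness and power are not given.

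**Planned size.** The same section describes 96 participants "in two separate studies (i.e., n=48 per study". Section 3.2.2 agrees: "Recruitment will stop when approximately 48 evaluable subjects complete each phase of the study".

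**The concern.** The promise of a correction and an apparently uncorrected threshold stand in one paragraph, so it is unclear at what level the primary comparison will be tested. If the rule stays open, several things can be settled after the data are seen: whether the primary test belongs to the corrected family, which of the two primary quantities counts, and which method is used. A primary result with p between 0.025 and 0.05 would succeed with no correction and fail under a two-test Bonferroni rule.

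The detectable effect is also the only justification that the plan gives for its size. If it belongs to a different test, or to a different number of subjects, readers are given too favourable a view of what each cycle can show.

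**Working it through.** **Inputs.** Critical t 1.99, d = 0.74, 48 per group and 48 per study, all from Section 6.4; about 48 evaluable per cycle, from Section 3.2.2. Assumed because the documents are silent: 1:1 allocation, hence 24 per arm; Bonferroni as the form of correction; 2 to 4 tests as the family. The range of 2 to 4 reflects the endpoints named: two primary quantities, a third test with the knowledge score, and up to a fourth in Cycle B with the 4-week assessment.

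**Method.** Two-sample t-test with n per arm: df = 2n − 2, noncentrality = d × √(n/2), critical value t(1 − α/2; df), and power from the noncentral t distribution.

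**Step 1: reproduce the plan's figures.** With n = 48, df = 94 and √(48/2) = 4.899.
- t(0.975; 94) = 1.986, which rounds to the stated 1.99.
- The d detectable with 95% power is 0.743, which rounds to the stated 0.74.
- At two-sided 5% and the same n, 80% power would give d = 0.58 and 90% power d = 0.67. Neither matches, so 95% is the implied power.
- A two-sided 5% level split over two tests would give t = 2.28, which also does not match.

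**Step 2: planned size, no correction.** With n = 24, df = 46 and √(24/2) = 3.464.
- t(0.975; 46) = 2.013, so 1.99 is not the threshold for a cycle of 48.
- Detectable d is 0.83 at 80% power and 1.06 at 95% power.
- At d = 0.74 the noncentrality is 0.74 × 3.464 = 2.563 and power is 70.9%, against 94.8% with 48 per group.

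**Step 3: add a Bonferroni split** (α = 0.05/m, two-sided).

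| Tests m | 48/group: t | d at 95% power | Power at 0.74 | 24/arm: t | d at 80% power | d at 95% power | Power at 0.74 |
|---|---|---|---|---|---|---|---|
| 1 | 1.99 | 0.74 | 95% | 2.01 | 0.83 | 1.06 | 71% |
| 2 | 2.28 | 0.80 | 91% | 2.32 | 0.92 | 1.15 | 60% |
| 3 | 2.44 | 0.84 | 88% | 2.48 | 0.96 | 1.20 | 54% |
| 4 | 2.55 | 0.86 | 86% | 2.60 | 1.00 | 1.24 | 49% |

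**Step 4: separate the two effects at d = 0.74.** Going from 48 per group to 24 per arm costs 94.8 − 70.9 = 23.9 percentage points. At 24 per arm, the split then costs a further 70.9 − 59.9 = 11.0 points for two tests, or 70.9 − 49.2 = 21.7 points for four.

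**The case against.** A reader might infer that any correction must raise the threshold, so that 1.99 and 0.74 contradict the plan's own rule. The documents do not support that. Section 6.4 does not say that alpha is split or that the primary test is in the corrected family. A fixed-sequence rule also corrects for multiple comparisons, and it leaves the first test at the full 5%. What stands is narrower: no alpha-splitting correction is in the figures, and the plan does not say whether one applies.

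A reader might also blame multiplicity for most of the lost power. On the plan's stated 48 per group, a split over 2 to 4 tests leaves power at d = 0.74 between 91% and 86%. The fall from 95% to 71% comes from the sample size alone.

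The number of tests is open to argument as well. Section 6.3.2 states one hypothesis for the interaction score, and for Cycle B (there called Cycle 2) it names only the baseline-to-Virtual comparison between groups. Section 6.4 specifies one ANOVA for Live Interaction data and one for questionnaire data. Two to four tests is therefore an illustration. A larger family formed by pooling the cycles would sit badly with Section 6.4, which calls them separate studies, and Section 9.6, which describes two distinct populations.

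Finally, 1.986 is also the one-sided 2.5% value, so by arithmetic alone it could be a one-sided 5% level split over two tests. Nothing in the documents mentions one-sided testing or such a split, and a two-group ANOVA F test corresponds to a two-sided t-test.

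**Conclusion.** The point holds as a gap in specification together with a mismatched calculation. The promised correction has no method, family or number of tests, while more than one primary quantity is named. The stated critical t and detectable effect describe a single uncorrected two-sided 5% test on 96 subjects at an unstated 95% power, which is not the test that either cycle of 48 will run.

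The sample-size mismatch is the part that does not depend on how the correction is read: for any 1:1 comparison within a cycle of 48, the stated 0.74 has about 71% power at best under a two-sided 5% test without covariates. The additional loss to 60% to 49% is conditional on a Bonferroni rule over 2 to 4 tests.

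The figures assume 1:1 allocation and 48 analysed per cycle. The intention-to-treat set could be somewhat larger than the evaluable set, but the documents give no rate from which to compute that. They also leave out any gain from baseline adjustment, because no correlation between baseline and outcome is given.

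**What to change.** In Sections 6.1, 6.3.2 and 6.4:

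1. Name one primary test per cycle: the between-arm difference in the post-treatment Police Interaction Assessment (Live in Cycle A, Virtual in Cycle B), adjusted for the baseline assessment, at two-sided 0.05 within each cycle. This merges the two primary quantities into one analysis, so alpha need not be divided between overlapping versions of the same score.
2. Replace the general promise of correction with a fixed order: test the secondary endpoints only if the primary is significant, for example the knowledge score and then, in Cycle B, the 4-week assessment. The order is a choice for the sponsor; what matters is that it is written down before analysis.
3. Restate alpha, sidedness, power, critical t and detectable d for that test at 24 per arm: about 2.01 and d = 0.83 at 80% power, before any gain from baseline adjustment. State the allocation ratio.

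The cost is wording only; no visit, measure or subject is added. There are two downsides: no secondary endpoint can be claimed if the primary fails, and the published detectable effect becomes less favourable than 0.74.
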